## 3.7. Randomisation

For each of the studies, we will utilise a block randomisation procedure to allocate participants to one of 2 experimental arms. Random numbers will be generated using Stata 13.0 and each consecutive number that is generated will be printed and put inside an opaque envelope, which will then be sealed. Envelopes will be numbered in an ascending sequence. Once a participant has provided informed consent, the researcher will take the relevant envelope, open it, and use the number contained in it to allocate the participant to one of the 2 experimental groups. Researchers conducting participant recruitment will not be involved in this randomisation procedure in order to avoid recruitment bias.

## 3.8. Statistical Analysis

### 3.8.1. Descriptive statistics

We will report the number of participants approached that did not meet our participant inclusion criteria, as well as the main reason for exclusion (as a fraction of the total number of participants that were excluded). In addition, we will report the proportion of participants who were approached and refused to take part in our study as a fraction of the total number of participants approached (i.e., refusal rates).

Moreover, we will report the following information for each experimental group and for each study:

- Main demographic characteristics: percentage of participants according to age group, ethnic group, employment status, educational attainment, marital status, number of children, smartphone or tablet ownership, and previous history of depression
- Proportion of participants answering *Yes* to any of the Whooley questions
- Proportion of participants scoring at each interval of the EPDS: (i) 0 and 9 points; and (ii) 10 and 12 points; and (iii) 13 points or above
- Proportion of participants scoring 2 or 3 points on question 10 of the EPDS
- Mean time spent on each survey questionnaire (i.e., personal demographic information, Whooley questions, and the EPDS)
- Proportion of participants making each type of request for help
- Mean time spent dealing with requests for help
- Breakoff rates and reasons for breakoff

### 3.8.2. Inferential statistics

#### 3.8.2.1. Positive predictive value (PPV)

We will calculate the PPV of the Whooley questions by dividing the total number of pregnant women who answered *Yes* to any of the Whooley questions and scored 10 points or higher on the EPDS by the total number of women who answered *Yes* to any of the Whooley questions. We will present this value in percentage form.

#### 3.8.2.2. Negative predictive value (NPV)

We will calculate the NPV of the Whooley questions by dividing the total number of pregnant women who answered *No* to both Whooley questions and scored 9 points or lower on the EPDS by the total number of women who answered *No* to both Whooley questions. We will present this value in percentage form.

#### 3.8.2.3. False omission rate (FOR)

We will calculate the FOR of the Whooley questions by dividing the total number of pregnant women who answered *No* to both Whooley questions and scored 10 points or higher on the EPDS by the total

number of women who answered *No* to both Whooley questions. We will present this value in percentage form.

#### *3.8.2.4. Data equivalence*

We will determine data equivalence between the two EPDS layouts (i.e., scrolling and paging) by testing for statistically significant differences in the mean overall scores on the EPDS. For this, we will conduct a t-test.

In addition, we will compare the proportion of women scoring (i) between 10 and 12 points, and (ii) 13 or more points between the 2 experimental groups using a t-test.

#### *3.8.2.5. Time needed to complete the survey questionnaires*

We will compare the mean time needed by participants to complete the survey questionnaires between the experimental groups. For this we will conduct a t-test.

#### *3.8.2.6. Data completeness*

We will compare the proportion of complete records between the experimental groups using a t-test.

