#### *3.8.2.7. Proportion of requests for help*

We will compare the proportion of participants making requests for help between the experimental groups. For this, we will conduct a t-test for each category in this endpoint: (i) one request; (ii) between 2 and 4 requests; and (iii) 5 or more requests.

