#### *3.8.2.8. Drop-out rates*

We will compare the proportion of potential participants who drop-out the study before 6 months (out of the total number of participants enrolled in the study) between the experimental groups.

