#### *3.8.2.9. Adherence to sampling protocols*

We will compare the proportion of participants who completed 100% of the expected assessments between the experimental groups using a t-test.

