#### *3.8.2.10. Timeliness of data collection*

We will compare the proportion of participants who completed the pre-specified assessments after receiving a prompt between the experimental groups using a t-test.

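### Proportions are compared with t-tests: harmless for common outcomes, but for sparse ones the test gives no result with zero events and an exact test or score interval would serve better (minor)

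*Combined protocol and SAP*

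**What the plan says.** Section 3.8.2 names a t-test for the following comparisons of proportions:

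- **EPDS bands (3.8.2.4).** The proportions scoring 10 to 12 points and "13 or more points between the 2 experimental groups using a t-test".
- **Data completeness (3.8.2.6).** "We will compare the proportion of complete records between the experimental groups using a t-test".
- **Help requests (3.8.2.7).** "we will conduct a t-test for each category in this endpoint", the categories being one, 2 to 4, and 5 or more requests.
- **Adherence (3.8.2.9).** "We will compare the proportion of participants who completed 100% of the expected assessments between the experimental groups using a t-test".
- **Timeliness (3.8.2.10).** The proportion who "completed the pre-specified assessments after receiving a prompt between the experimental groups using a t-test".

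For drop-out, 3.8.2.8 says "We will compare the proportion of potential participants who drop-out the study before 6 months" and names no test. The t-tests on mean EPDS score (3.8.2.4) and completion time (3.8.2.5) concern continuous outcomes and are not at issue here. Section 3.8.2 names no chi-square or exact test and plans no confidence interval for any between-group difference.

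Two definitions matter. In the tablet study, validation prevents unanswered items, so completeness is measured by breakoff alone (3.3.1.1.7). In the app (BYOD) study, completeness is the share of assessment records that are complete among complete plus attempted records (3.3.1.2.5), so one woman contributes several records.

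**The concern.** A t-test on 0/1 data relies on the sample proportions being roughly normal with a usable variance estimate. That is safe when both outcomes are reasonably frequent, but some of these outcomes could be close to zero in both arms. With forced answers, tablet breakoff may be very rare, and section 2.1.3 expects no difference between layouts. Five or more help requests on a short questionnaire may be rare too.

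With no events in either arm the planned analysis returns nothing, although no breakoffs among 300 women would be an informative feasibility result. With only a few events, a reader cannot tell whether a p-value just below 0.05 reflects the data or the choice of test. App-study completeness has a different problem: records from the same woman are correlated, and a t-test on pooled records would treat them as independent.

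**Working it through.** **Inputs.** Section 3.6 gives at least 300 women in the tablet study and at least 200 in the app study. Section 3.7 describes blocked allocation to two arms without a ratio; I assume 1:1, hence 150 and 100 per arm. No alpha is stated for these comparisons; I assume two-sided 0.05. The documents give no event rates for breakoff or help requests, so rates are shown over a range.

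**The plan's own figure.** The app-study size is tied to a proportion: n = 1.96² × 0.5 × 0.5 / 0.10² = 96.04, which reproduces the stated 96 per arm.

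**Step 1: common outcomes.** Over all possible 2×2 tables, the t-test and Pearson chi-square never disagree at 0.05 with 150 per arm. With 100 per arm they disagree only for 26 v 39 and its mirror, 61 v 74. At the 12% prevalence assumed in section 3.6, the exact type I error of the t-test is 5.0% (150 per arm) and 5.1% (100 per arm).

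**Step 2: type I error when events are rare (150 per arm, exact enumeration).**

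| True rate in both arms | t-test | Fisher |
|---|---|---|
| 0.5% | 0.7% | below 0.1% |
| 1% | 2.9% | 0.2% |
| 2% | 4.6% | 1.2% |
| 5% | 4.8% | 2.4% |

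The t-test does not exceed its nominal level here. Its maximum over all rates examined is 5.7%, at a rate of 50%.

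**Step 3: no events at all.** The probability that neither arm has an event is (1 − rate)^(total n). At a rate of 0.5% this is 0.995^300 = 0.222 with 150 per arm and 0.995^200 = 0.367 with 100 per arm. At 1% it falls to 0.99^300 = 0.049 and 0.99^200 = 0.134. In those trials the t statistic is 0/0 and a t interval collapses to 0 to 0. The Newcombe limits are ± z²/(n + z²) = ± 3.84/153.84, or ± 2.5 points with 150 per arm, and ± 3.84/103.84, or ± 3.7 points with 100.

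**Step 4: few events.** For 0 v 4 of 150:

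- Difference: 4/150 = 0.0267.
- Pooled variance: half of 0.0267 × 0.9733 × 150/149, which is 0.01307.
- Standard error: √(0.01307 × 2/150) = 0.0132.
- t = 2.02 on 298 degrees of freedom, p = 0.044.
- Fisher: 2 × (150·149·148·147)/(300·299·298·297) = 0.12.

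Other splits at 150 per arm:

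| Events | t-test p | Fisher p | Barnard p | Smaller expected count |
|---|---|---|---|---|
| 0 v 4 | 0.044 | 0.12 | 0.045 | 2 |
| 0 v 5 | 0.024 | 0.060 | 0.025 | 2.5 |
| 1 v 7 | 0.032 | 0.067 | 0.037 | 4 |
| 2 v 9 | 0.032 | 0.061 | 0.033 | 5.5 |
| 3 v 10 | 0.047 | 0.085 | 0.050 (0.0495) | 6.5 |

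Boschloo's exact test is mixed: 0.100 for 0 v 4 and 0.048 for 0 v 5.

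**Step 5: interval coverage (exact enumeration, nominal 95%).**

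| True rates | Per arm | t interval | Newcombe |
|---|---|---|---|
| 1% v 3% | 150 | 92.3% | 97.0% |
| 0.5% v 2% | 100 | 86.4% | 99.6% |
| 0.5% v 2% | 150 | 94.0% | 98.5% |
| 1% v 1% | 150 | 97.1% | 99.2% |

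The shortfall appears when the true rates differ. In the second row, 8.0 of the 13.6 points of non-coverage come from trials with no events (0.995^100 × 0.98^100 = 0.080), where the collapsed interval excludes the true difference. For 0 v 4 of 150 the t interval is 0.1 to 5.3 points and the Newcombe interval −0.3 to 6.7.

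**The case against.** A reader might infer that the t-test produces false positives when events are rare. The documents and the arithmetic do not support that: in step 2 its type I error stays below 5%. The differing verdicts in step 4 arise largely from Fisher's conservatism. Barnard's exact test agrees with the t-test for all five splits listed, so it would be wrong to say that exact methods as a class contradict the planned test. This part of the defence stands. Nor would the usual expected-count rule remove every disagreement with Fisher: for 2 v 9 and 3 v 10 it selects chi-square, which gives the t-test's verdict.

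A reader might also infer that the plan will report poor confidence intervals. It plans none for these differences; the coverage figures describe an interval that an analyst would naturally attach to a t-test. They support adding a better interval, and do not show an error in one the plan contains.

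Third, one might expect 100% adherence to break the test, because the momentary arm has 6 × (4 × 3 + 2) = 84 assessments (72 momentary and 12 EPDS, section 3.5.2.2.2) against 6 in the other arm. Sparseness in one arm alone does not do this. A pooled t-test still computes, and at 100 per arm 0 v 6 already gives t-test p = 0.013 and Fisher p = 0.029, the same verdict.

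Finally, sparseness is not documented, and the primary objectives are feasibility (2.1.1, 2.2.1). Both are correct and limit the weight of the point. They do not answer the no-event case, nor the repeated records in app-study completeness.

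**Conclusion.** The point holds in a limited form and is minor. Five sections name a t-test for proportions. For common outcomes the choice is nearly immaterial, and for rare ones type I error is not inflated. What remains is threefold. The test gives no result when neither arm has an event (22% of trials at a 0.5% rate with 150 per arm, 37% with 100). With a handful of events the verdict turns on which test was written down. A t-based interval can under-cover when rare rates differ (92% and 86% in the two cases above). Separately, app-study completeness should not be analysed as independent yes/no data.

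This rests on 1:1 allocation, full recruitment, a two-sided 0.05 level, and event rates near or below about 3% for the affected outcomes. That last assumption is plausible for breakoff and for 5 or more help requests, but the documents give no figure. The criticism of the t-test does not extend to drop-out, where the gap is that no test is named.

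**What to change.** In 3.8.2.4 (EPDS bands), 3.8.2.6 (tablet study), 3.8.2.7, 3.8.2.9 and 3.8.2.10, replace the t-test for participant-level proportions with a chi-square test, using an exact test when an expected count is below 5. Name the exact test in advance, since step 4 shows that Fisher, Boschloo and Barnard can differ. Make the risk difference with a Newcombe (score) 95% confidence interval the main reported result. Apply the same to drop-out in 3.8.2.8.

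For app-study data completeness, either reduce the records to one summary per woman before comparing arms, or use a method that allows for clustering of records within women.

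The cost is a few sentences of SAP wording, with no change to design, data collection or sample size. The statistical price is that Fisher's test is markedly conservative for rare events (actual size about 0.2% to 1.2% at rates of 1% to 2% with 150 per arm), which is why the emphasis should fall on the interval and not on the p-value.

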#### *3.8.2.7. Proportion of requests for help*

We will compare the proportion of participants making requests for help between the experimental groups. For this, we will conduct a t-test for each category in this endpoint: (i) one request; (ii) between 2 and 4 requests; and (iii) 5 or more requests.

#### *3.8.2.8. Drop-out rates*

We will compare the proportion of potential participants who drop-out the study before 6 months (out of the total number of participants enrolled in the study) between the experimental groups.

#### *3.8.2.9. Adherence to sampling protocols*

We will compare the proportion of participants who completed 100% of the expected assessments between the experimental groups using a t-test.

#### *3.8.2.10. Timeliness of data collection*

We will compare the proportion of participants who completed the pre-specified assessments after receiving a prompt between the experimental groups using a t-test.

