### 2.2.2. Secondary Objectives

- To assess differences in drop-out rates between the participants allocated to the retrospective assessment strategy (i.e., EPDS), and those allocated to the retrospective plus momentary assessment strategy (i.e., EPDS complemented with the EMA of mood, sleep, energy, enjoyment and worry).
- To assess differences in participants' adherence to sampling protocols between a retrospective assessment strategy (i.e., EPDS), and a retrospective plus momentary assessment strategy (i.e., EPDS complemented with the EMA of mood, sleep, energy, enjoyment and worry). We will achieve this by comparing the proportion of participants in each group that complete 100% of the expected assessments.
- To assess differences in usage patterns of the app between a retrospective assessment strategy and a retrospective plus momentary assessment strategy, including additional voluntary self-reporting, time spent using the app, number of interactions with other sections of the app, time to complete the self-assessments, and other ancillary usage data
- To assess differences in participants' acceptance of the app between a retrospective assessment strategy and a retrospective plus momentary assessment strategy through a post-study self-administered questionnaire

- To assess differences in timeliness of data collection between a retrospective assessment strategy and a retrospective plus momentary assessment strategy. We will achieve this by comparing the proportion of participants completing their assessments in response to a prompt displayed on their mobile devices between the two groups
- To assess differences in data completeness between a retrospective assessment strategy and a retrospective plus momentary assessment strategy. We will achieve this by comparing the proportion of complete records between the two groups
- To evaluate the impact of a momentary assessment technique of the EPDS scores by comparing the EPDS scores obtained at the start of the sampling period and the EPDS scores obtained at the end of this period. This will be assessed in the *retrospective plus momentary assessment* condition only
- To assess if feedback provided by a healthcare practitioner influences participants' and clinicians' engagement, acceptance and perceived usefulness of an app used for the remote and longitudinal monitoring of mood symptoms throughout pregnancy

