### 3.3.1.2.3. Adherence to sampling protocols

The proportion of participants who complete 100% of the expected assessments over the duration of the study.

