### 3.3.1.2.4. Timeliness of data collection

Each pre-specified assessment will be preceded by a prompt. Timeliness of data collection will be defined as the proportion of participants who complete the pre-specified assessments immediately after receiving this prompt.

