### 3.5.2.2.1. Retrospective assessment

Participants in this condition will be asked to complete the EPDS once a month for 6 months. The day on which participants are required to complete the EPDS will be selected at random from each calendar month, and with no less than 2 weeks in between 2 consecutive sampling periods. On that day, we will select a random time between 10.00 and 22.00 to administer the EPDS. At that time, a notification will be displayed on a participant's phone asking her to complete the EPDS. They will then be able to accept the request or reject it. Outside the sampling period, participants will be allowed to complete as many assessments as they wish to. However, during the sampling period, participants will not be allowed to complete any additional assessments.

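### The timeliness analysis counts any completion after a prompt, while the endpoint requires immediate completion without a time window or per-woman rule; a yes/no per woman over 6 versus 84 assessments is also not comparable between arms

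*Combined protocol and SAP*

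**What the plan says.** Timeliness is a secondary objective of the BYOD study, listed separately from adherence and data completeness. It is worded in three ways:

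- Objective (2.2.2): "comparing the proportion of participants completing their assessments in response to a prompt displayed on their mobile devices between the two groups".
- Endpoint (3.3.1.2.4): "Timeliness of data collection will be defined as the proportion of participants who complete the pre-specified assessments immediately after receiving this prompt".
- Analysis (3.8.2.10): "We will compare the proportion of participants who completed the pre-specified assessments after receiving a prompt between the experimental groups using a t-test".

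The endpoint section also says: "Each pre-specified assessment will be preceded by a prompt". For the retrospective arm, 3.5.2.2.1 adds that "during the sampling period, participants will not be allowed to complete any additional assessments", and 3.5.2.2.2 sets the same restriction for the momentary arm. Voluntary assessments are allowed outside the sampling period, but these are not pre-specified assessments.

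Adherence is defined in 3.3.1.2.3 as "The proportion of participants who complete 100% of the expected assessments over the duration of the study", and 3.8.2.9 compares that proportion between arms.

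No section gives a number of minutes or hours for a response to count as immediate, an expiry time for a prompt, or the number of a woman's assessments that must be prompt for her to count as timely.

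**The concern.** The analysis sentence contains no time element. If a scheduled assessment always follows its prompt, then having been completed after a prompt says only that it was completed. An analyst working from 3.8.2.10 alone would report completion under the heading of timeliness. An analyst working from 3.3.1.2.4 would have to invent a cut-off, possibly after seeing the data.

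Delay matters for this design. The Background justifies EMA as momentary data less exposed to recall bias, so how soon a woman answers bears on whether her answer is momentary. The arms also differ greatly in the number of prompts they receive, so a measure that classifies each woman once over all her prompts may reflect the schedule and not her behaviour.

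**Working it through.** The plan states no sample size, power or expected rate for timeliness, so there is no figure of its own to reproduce. The check compares the wordings and then counts prompts.

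**Step 1. What 3.8.2.10 counts.** By 3.3.1.2.4 a prompt comes before each pre-specified assessment. By 3.5.2.2.1 and 3.5.2.2.2 additional assessments are barred during the sampling period. A completed scheduled assessment has therefore always been completed after its prompt, and the condition in 3.8.2.10 excludes none of them.

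**Step 2. Relation to adherence.** Let *c* be the probability that a scheduled assessment is completed, *q* the share of completed assessments that are immediate, and *k* the number scheduled. Assume independence, and assume that a woman counts only if all *k* qualify. Then

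- adherence = c^k
- timeliness = (c × q)^k

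Under the literal wording of 3.8.2.10, q = 1 and the two are equal. Under the endpoint definition q can be below 1 and they separate. With assumed c = 0.95 and k = 6, adherence is 0.95^6 = 0.735, and timeliness is:

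| q (assumed) | (0.95 × q)^6 |
|---|---|
| 1.0 | 0.735 |
| 0.9 | 0.391 |
| 0.8 | 0.193 |
| 0.5 | 0.012 |

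**Step 3. Scheduled assessments per woman.**

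- Retrospective arm (3.5.2.2.1): one EPDS a month for 6 months = 6.
- Momentary arm (3.5.2.2.2): each month 2 EPDS plus 4 days × 3 EMA = 14; 6 × 14 = 84.

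**Step 4. What an all-or-none count does.** Suppose the chance *p* of a timely response to a prompt is the same in both arms and independent across prompts. The proportion of women counted as timely is p^6 against p^84:

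| p (assumed) | Retrospective, p^6 | Momentary, p^84 |
|---|---|---|
| 0.90 | 53.1% | 0.01% |
| 0.95 | 73.5% | 1.3% |
| 0.98 | 88.6% | 18.3% |
| 0.99 | 94.1% | 43.0% |

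Promptness per prompt is identical by construction, so the whole gap comes from the number of prompts. Putting *immediately* back into 3.8.2.10 does not remove it.

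**The case against.** The strongest reply is that 3.8.2 routinely abbreviates endpoints defined in 3.3.1. The data completeness analysis, for example, mentions only complete records and needs the endpoint section to be understood. Read together with 3.3.1.2.4, the timeliness analysis is plainly meant to capture promptness. That stands, and it rules out saying that the plan has no intention of measuring timeliness.

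Three stronger conclusions that a reader might draw are not supported:

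- *The timeliness test simply repeats the adherence test.* Adherence requires 100% of expected assessments, whereas no timeliness wording states a threshold. The two coincide only if 3.8.2.10 is taken literally and is also read as requiring all assessments.
- *EMA answers nearly four hours late would count.* The 4-hour periods in 3.5.2.2.2 govern when prompts are sent. The documents do not say how long a prompt stays open, so the possible delay is unknown.
- *The objective cannot be answered.* The objectives already include usage data from the app, and nothing shows that response times would be unavailable.

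The wording of the objective may also carry its own meaning. Women can accept or reject a notification, and the documents do not say whether a scheduled assessment can still be done later after a prompt is rejected or ignored. If it can, responding to the prompt is narrower than completing the assessment. This is a further reason to settle on one definition.

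Finally, section 2.2.3 states no hypothesis about timeliness, and 3.6 sizes the BYOD study on adherence. No primary conclusion depends on this outcome, which limits the importance of the point. The reply does not supply the missing window or counting rule, and it does not deal with 6 versus 84 prompts.

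**Conclusion.** The point holds in a limited form. The analysis text does not match the endpoint it is meant to analyse, and the endpoint cannot be calculated as written because the response window and the per-woman rule are missing. Taken literally, 3.8.2.10 measures completion. Overlap with adherence is conditional on an all-assessments reading that the plan does not state.

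The issue goes beyond a dropped word, because a single yes/no per woman is not comparable between schedules of 6 and 84 assessments. The illustration of 73.5% versus 1.3% rests on three assumptions: an all-or-none count, a per-prompt probability of 0.95 in both arms, and independence between prompts. Across the assumed range from 0.90 to 0.99 the gap runs from 53.1% versus 0.01% to 94.1% versus 43.0%. Correlation between a woman's responses would change these figures. A different threshold would also change them, which is why the rule has to be written down.

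This is a minor issue in one secondary outcome of a feasibility study, worth correcting before the data are analysed.

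**What to change.** 1. Use one definition in 2.2.2, 3.3.1.2.4 and 3.8.2.10.
2. Define timeliness from the app's time stamps as the delay from prompt to start of the assessment, and fix before analysis the window within which a start counts as in time.
3. Compare arms on the assessment that both share, the first scheduled EPDS of each month. Report EMA delays descriptively in the momentary arm.
4. Report the share started in time in two ways: over all prompts, with missed prompts counted as not in time, and among answered prompts. Summarise median delay among answered prompts only. This keeps promptness apart from completion and avoids an undefined delay for women who answer no prompt.

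The cost is a wording change, the choice of a window, and retention of the notification and response time stamps. Reporting delay as well as the share in time makes the choice of window less critical. One limitation should be stated: in the first month the opening EPDS of the momentary arm comes at the start of the sampling period, before that arm has built up experience of EMA, so any effect of EMA on promptness would be expected mainly in later months.
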